2.2 Secondary Objectives

- To assess the change in CD8+ TIL density from pre-treatment Transurethral Resection of Bladder Tumor (TURBT) to post-treatment Radical Cystectomy (RC) tissues separately in patients treated with nivolumab or combination of nivolumab/lirilumab.
- To assess percentage (%) change in CD8+ TIL density from pre-treatment TURBT to post-treatment RC tissues separately in patients treated with nivolumab and combination of nivolumab/lirilumab.
- To describe the rate of patients in each cohort who do not get RC within 6 weeks after completion of neoadjuvant treatment specifically and directly related to treatment-related adverse events (AEs).
- To assess the antitumor efficacy of nivolumab and combination of nivolumab/lirilumab as measured by pathologic complete (pT0N0) and partial (<pT2N0) response rate in the two cohorts.
- To assess the rate of recurrence-free survival (RFS) at the two-year time point from the time of registration in patients treated with nivolumab and combination of nivolumab/lirilumab.

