8.2 Duration of Follow-Up

Patients will be followed for adverse events for 100 days after their last dose of neoadjuvant treatment. Adverse events may be reviewed at the next visit \geq 100 days after last dose of neoadjuvant therapy or phone follow-up may be done to review adverse events. However, if a patient experiences an adverse event $>$ 100 days after their last dose of study medication that is felt to be, in the opinion of the investigator, possibly, probably or definitely related to study therapy, the adverse event should be reported.

Patients will be followed clinically and radiographically per standard of care (3 -6 months) at the discretion of the treating physician for at least 2 years post-cystectomy or when study-wide follow-up ends. Date of diagnosis for progression, first subsequent therapy and survival shall be reported. Phone follow-up may also be done for patients unable or unwilling to return for follow-up evaluations.

If a patient is removed from treatment for reason(s) other than progression, follow with regular tumor assessments per standard of care until progression or start of new treatment.

For patients who are registered but do not receive any protocol therapy, baseline and follow-up information per Section 11 will be collected.

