13.2.3 Additional Secondary Objectives

1. The average percentage (%) change in the CD8+ TIL density from TURBT to RC in each of the two cohorts. Each individual patient's percent change will be defined as $[(\text{Cystectomy TIL Density}) - (\text{TURBT TIL Density})] / (\text{TURBT TIL Density})$.
2. Proportion of patients in each cohort who do not get a radical cystectomy specifically and directly related to treatment related AEs within 6 weeks of the last dose of neoadjuvant treatment.
3. Proportion of patients with pathologic complete (pT0N0) and partial (<pT2N0) response in the two cohorts.
4. Proportion of patients who are alive and free of disease in each cohort at 2 years from registration.

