### 3.2. Secondary Objectives

The secondary objectives of this study are:

- To assess the change in CD8+ TIL density from pre-treatment Transurethral Resection of Bladder Tumor (TURBT) to post-treatment Radical Cystectomy (RC) tissues separately in patients treated with nivolumab or combination of nivolumab/lirilumab.
- To assess percentage (%) change in CD8+ TIL density from pre-treatment TURBT to post-treatment RC tissues separately in patients treated with nivolumab and combination of nivolumab/lirilumab.
- To describe the rate of patients in each cohort who do not get RC within 6 weeks after completion of neoadjuvant treatment specifically and directly related to treatment-related adverse events (AEs).
- To assess the antitumor efficacy of nivolumab and combination of nivolumab/lirilumab as measured by pathologic complete (pT0N0) and partial (<pT2N0) response rate in the two cohorts.
- To assess the rate of recurrence-free survival (RFS) at the two-year time point from the time of registration in patients treated with nivolumab and combination of nivolumab/lirilumab.
- To assess the prognostic and predictive value of the expression of baseline immunohistochemistry (IHC) markers of interest (e.g. PD-1, PD-L1, PD-L2, NKG2D, KIR2DL1/2/3), and change in expression, for pathologic partial and complete tumor response (defined by cystectomy pathologic staging <pT2N0 and pT0N0, respectively), in patients treated with nivolumab and combination of nivolumab/lirilumab.
- To assess the prognostic and predictive value of peripheral blood mononuclear cell (PBMC) T-cell subset status (%CD4+ T-cells, %CD8+ T-cells, %Treg T-cells, %Myeloid Derived Suppressor Cells, %Natural Killer cells, etc.) and change in status, as assessed by flow cytometry analysis, for pathologic partial and complete tumor response (defined by cystectomy pathologic staging < pT2N0 and pT0N0, respectively), in patients treated with nivolumab and combination of nivolumab/lirilumab.

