## 4. STUDY DESIGN

### 4.1. General Study Design and Plan

This is a Phase Ib open-label clinical trial for patients with cisplatin-ineligible MIBC (T2-T4a, N0-N1, M0). Patients will be sequentially enrolled first into Cohort 1 treated with nivolumab alone (N=12). In the absence of the occurrence of high rate of treatment related AEs as defined in protocol Section 5.4 and 13.1.1 with neoadjuvant nivolumab treatment, the study will proceed with enrollment into Cohort 2 of neoadjuvant treatment with combination nivolumab/lirilumab. (In both cohorts, neoadjuvant treatment must start within 8 weeks of transurethral resection of the first TURBT that showed muscularis propria invasion). Each group will receive a total of 4 weeks (week 0 and 4) of neoadjuvant therapy followed by radical cystectomy (RC) with bilateral (standard or extended) pelvic lymph node dissection (PLND).

The RC with bilateral (standard or extended) PLND will occur as soon as possible but within 6 weeks after the last neoadjuvant dose in either cohort.

Off treatment visit will occur approximately 30 days following cystectomy (cystectomy is not performed, Off Treatment visit should be performed at next scheduled appointment or treating physician discretion, as clinically indicated) and patients will be followed for 100 days after neoadjuvant treatment for AEs. Adverse events may be reviewed at the next visit  $\geq$  100 days after last dose of neoadjuvant therapy or phone follow-up may be done to review adverse events.

Patients will be followed clinically and radiographically for at least 2 years post-cystectomy or when study-wide follow-up ends per standard of care. Date of diagnosis for recurrence, first subsequent therapy and survival shall be reported. Phone follow-up may also be done for patients unable or unwilling to return for follow-up evaluations.

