#### **7.6.6.2. Secondary Endpoint, Patient who Did not Get Radical Cystectomy Due to AE**

The proportion of patients in each treatment cohort who do not get radical cystectomy specifically and directly related to treatment related AEs within 6 weeks of the completion of neoadjuvant treatment, will be reported along with exact binomial 90% confidence intervals for each cohort and compared between the two cohorts using Fisher's exact test. This is one of secondary objective endpoints.

The Identification of the AEs that cause patients do not get radical cystectomy by selecting "Caused Study Discontinuation" in AE CRF page, and with related to Nivolumab/Lirilumab, and patients do not have radical cystectomy surgery.

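### The SAP rule for surgery failure due to toxicity has no 6-week test, so cystectomies that toxicity delays past 6 weeks are not counted

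*SAP*

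**What the plan says.** Protocol 2.2 sets the objective: "To describe the rate of patients in each cohort who do not get RC within 6 weeks after completion of neoadjuvant treatment", where the cause is a treatment-related AE. SAP 3.2 repeats it. Protocol 13.2.3 words the endpoint as the proportion of patients "who do not get a radical cystectomy specifically and directly related to treatment related AEs within 6 weeks of the last dose of neoadjuvant treatment", and SAP 7.4.2.3 carries that text over. The window matches the design, in which surgery is to occur "as soon as possible but within 6 weeks after the last neoadjuvant dose in either cohort" (SAP 4.1).

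The first paragraph of SAP 7.6.6.2 restates the endpoint with its 6-week window. It plans exact binomial 90% confidence intervals per cohort and a Fisher's exact test between cohorts. The second paragraph says how cases are to be identified: "by selecting 'Caused Study Discontinuation' in AE CRF page", "and with related to Nivolumab/Lirilumab, and patients do not have radical cystectomy surgery". All three conditions must hold: the flag, drug attribution and no cystectomy.

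SAP 7.6.5 counts patients who receive a cystectomy, without timing. SAP 2.1 gives the SAP precedence over the protocol's statistical section, and SAP 8 declares no departures from the protocol's analyses.

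**The concern.** The objective is about timing. A patient whose immune-related toxicity moves surgery to week 8 or week 12 has not had surgery within 6 weeks and should be counted. The SAP rule asks only whether surgery happened, so that patient is left out.

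The discontinuation flag is a second filter. Missing surgery is not the same as leaving the study. Protocol 8.2 keeps such patients under observation: "If a patient is removed from treatment for reason(s) other than progression, follow with regular tumor assessments per standard of care". Protocol 5.3 provides an off-treatment visit when cystectomy is not performed. A patient who never reaches surgery because of toxicity but remains in follow-up may therefore carry no flag.

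This endpoint bears directly on whether the regimen can be given before curative surgery. Protocol 13.1 describes the study as evaluating feasibility and safety. Protocol 1.4 and 1.5.2 support the two-dose schedule partly on the ground that it leaves room for cystectomy within 6 weeks of the last dose. An endpoint that cannot register delay cannot test that expectation.

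**Working it through.** **1. The endpoint and the rule side by side.** Assume the toxicity is treatment-related in every row.

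| Patient | Endpoint (Protocol 2.2, SAP 3.2) | Rule (SAP 7.6.6.2) |
|---|---|---|
| Surgery by week 6 | Not a failure | Not counted |
| Surgery after week 6, delayed by toxicity | Failure | Not counted, because surgery took place |
| No surgery because of toxicity, stays in follow-up | Failure | Counted only if the discontinuation flag is ticked |
| No surgery because of toxicity, leaves the study | Failure | Counted |

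The second row is lost on the wording alone. The third depends on how sites complete the form.

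**2. Interval method.** The plan gives no figure for this endpoint. Protocol 13.2.1.1 and SAP 7.4.1 give maximum 90% interval widths of 0.51 and 0.36 for the primary endpoint, using the same method and cohort sizes. For x events in n patients, the Clopper-Pearson limits are:

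- lower = 5% quantile of Beta(x, n − x + 1), or 0 if x = 0
- upper = 95% quantile of Beta(x + 1, n − x)

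The widest intervals are 0.509 (6/12) and 0.361 (12/24), so the plan's figures are reproduced.

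**3. Effect of uncounted patients.** The documents give no rate of toxicity-delayed surgery, so these counts are assumptions.

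| Assumed true situation | SAP rule reports (90% CI) | Endpoint as defined (90% CI) |
|---|---|---|
| Cohort 1: 1 delayed | 0/12 (0 to 22.1%) | 1/12 = 8.3% (0.4 to 33.9%) |
| Cohort 2: 2 delayed | 0/24 (0 to 11.7%) | 2/24 = 8.3% (1.5 to 24.0%) |
| Cohort 2: 1 never operated and flagged, 3 delayed | 1/24 = 4.2% (0.2 to 18.3%) | 4/24 = 16.7% (5.9 to 34.2%) |

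With x = 0 the upper limit is 1 − 0.05^(1/n), which gives 0.221 for n = 12 and 0.117 for n = 24.

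**4. Effect on the Fisher test (two-sided).** Combining the first and third rows, p is 1.00 for 0/12 against 1/24 under the SAP rule, and 0.65 for 1/12 against 4/24 under the endpoint.

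**5. How likely a miss is.** If each patient has probability p of a toxicity-delayed operation, the chance of at least one uncounted patient is 1 − (1 − p)^n and the expected number is np.

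| Assumed p | Cohort 1 (n = 12): chance, expected | Cohort 2 (n = 24): chance, expected |
|---|---|---|
| 5% | 46%, 0.6 | 71%, 1.2 |
| 10% | 72%, 1.2 | 92%, 2.4 |
| 15% | 86%, 1.8 | 98%, 3.6 |
| 20% | 93%, 2.4 | 99.5%, 4.8 |

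**The case against.** The best defence is that the identification paragraph inherits the 6-week window from the paragraph above it, so that having no surgery means having none in time. The rule does not say this. Even if it is read that way, the discontinuation flag still excludes a patient who stays on study and is operated on late.

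A second defence is that the wording in Protocol 13.2.3 and SAP 7.4.2.3 is loose, and the 6 weeks could attach to the AEs instead of the surgery. The ambiguity is real, but Protocol 2.2 and SAP 3.2 place the window directly after the failure to have surgery, which settles the meaning.

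Third, the AE form, its completion instructions and the table templates are not in the documents. This stands against certainty about the flag: it may miss patients who remain in follow-up, but that cannot be shown. The loss of delayed surgeries does not depend on the form. No timing summary in the SAP text would recover them.

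Fourth, this is an additional secondary endpoint, no decision rule hangs on it, and the effect on the between-cohort test is small. With 1/12 and 2/24 the two rates are equal and p = 1. All of that is fair. It limits the consequence but does not make the derivation match the endpoint.

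**Conclusion.** The concern holds. As written, SAP 7.6.6.2 does not measure the endpoint in Protocol 2.2 and SAP 3.2: patients operated on after 6 weeks because of treatment-related toxicity are failures by definition but are not counted. SAP 8 does not declare the narrowing. Omitting these patients can only lower the reported rate, and it does so whenever such a patient occurs. The actual size cannot be derived from the documents. At these sample sizes one uncounted patient shifts the rate by 8.3 percentage points in Cohort 1 (1/12) and 4.2 in Cohort 2 (1/24). The harm is mainly to the per-cohort rates and their intervals, and less to the Fisher test. That the flag also loses never-operated patients is plausible but depends on a form not available here.

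**What to change.** Replace the identification paragraph in SAP 7.6.6.2 with a date-based derivation:

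- **Numerator:** treated patients with no cystectomy by the date of last neoadjuvant dose + 42 days (never operated on, or operated on later), where the recorded reason for delay or omission is an AE rated definite, probable or possible.
- **Denominator:** all treated patients. This is the safety population that SAP 7.6 already implies, but it should be stated here.
- **Flag:** remove the study-discontinuation condition.
- **Display:** show never-operated and delayed patients separately as well as combined, so that the source of the rate is visible.
- **Clarifications:** use the last-dose date as the single anchor in SAP 7.4.2.3 and 7.6.6.2, and say whether the ±3-day and holiday allowances in Protocol 7 and 11 apply to this 42-day cut for analysis.

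The cost is one SAP derivation change and its programming. Dose and surgery dates are already part of the study data. The reason for late or omitted surgery is not among the AE fields listed in Protocol 9.1 or SAP 6.1, so it would need a site query for the patients without cystectomy by day 42, out of 36 planned. Nothing in patient management changes.

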#### **7.6.6.3. AE Summary Analysis by System Organ Class and Preferred Term**

Treatment-emergent AEs (TEAEs) are those that occur after administration of the first study dose until 100 days after last dose of study medication. In the case where the start date of the AE is unknown, it will be assumed to be treatment-emergent. TEAEs will be summarized by System Organ Class (SOC) and preferred term (PT) using the Medical Dictionary for Regulatory Activities (MedDRA®). The latest version of MedDRA (V 20.0) will be used. The frequency of patients who experience TEAEs will be summarized by cohort and overall. Patients, having the same AE more than once per group, will be counted once for each PT and once within each SOC.

All AEs, TEAEs, treatment-related AEs, Grade 3 or higher treatment-related AEs, SAEs, TEAEs caused stopping study medications, TEAEs leading to early termination, fatal TEAEs will be summarized by cohort and overall group. Also, above AE categories will be summarized by SOC and PT as well.

Common Terminology Criteria for Adverse Events version 5.0 (CTCAE v5.0) will be used to manifest AE grade.

#### **7.6.7. Clinical Laboratory Data**

Numeric clinical laboratory data will be summarized at each visit (clinical data collection point) using descriptive statistics. Non-numeric laboratory tests will be summarized separately using frequency counts on unique responses. Individual change from baseline in lab values will be calculated and summarized descriptively. The Lab shift table will be displayed at each visit for each laboratory test.

### **7.6.8. Vital Signs Data**

Vital sign collected value and change from baseline will be summarized by visit and displayed by cohort and overall treatment group.

### **7.7. Efficacy Analysis**

All Efficacy analyses are performed for efficacy population except Recurrent-Free Survival and Overall Survival analyses. The RFS and OS analyses are performed for safety population.

#### **7.7.1. The mean change of CD8+ TIL density in each cohort**

There are 2 CD8+ TIL density readings for each patient. One is prior and another one is after study treatment. Patients obtained prior treatment CD8+ TIL density from TURBT. Patients obtained post treatment CD8+ TIL density from radical cystectomy. The mean change in CD8+ TIL density of each cohort will be calculated by averaging the change in TIL densities of all patients in the cohort.

In each cohort a one-sample Wilcoxon signed-rank test will be used to test whether the mean change in TIL density differs significantly from zero. This is key secondary objective (SAP section 7.4.2.1).

Additionally, the TIL density at radical cystectomy (post study treatment) will be compared between the two cohorts using a Wilcoxon rank sum test. This is the first exploratory objective (SAP section 7.4.3.1).

#### **7.7.2. The average percent (%) change of CD8+ TIL density in each cohort**

Each individual patient's percent change is defined as:

$$100 * [(Cystectomy TIL Density) - (TURBT TIL Density)] / (TURBT TIL Density).$$

The mean percent change of CD8+ TIL density from pre-treatment (TURBT) to post-treatment (radical cystectomy) samples in all 12 patients in Cohort 1 and all 24 patients in Cohort 2 will be calculated and compared between the two cohorts using a Wilcoxon rank sum test. This is one of secondary objective endpoints.

### **7.7.3. Pathology response in each cohort**

The proportion of patients in each treatment cohort with pathologic complete response (CR) and pathologic partial response (PR) will be reported along with exact binomial 90% confidence intervals for each cohort. This is one of secondary objective endpoints. Pathologic response (<ypT2N0M0) is defined by post-treatment radical cystectomy tumor stages with N0 and M0 status with the following T-stages: T0, Ta, Tis, T1.

The pathologic complete response (CR) is defined as: The pT0N0M0 is assigned at cystectomy tumor stage that based on bladder cancer TNM staging system. This stage indicates the patient is no evidence of primary tumor (T0) and no lymph node metastasis (N0).

The pathologic partial response (PR) is defined as: The stages that are less than T2N0M0 stage (<pT2N0M0) at cystectomy. Tumor stages with N0 and M0 status with the following T-stages: T0, Ta, Tis, and T1 are considered as partial response.

Pathologic non-response (NR) is defined by post-treatment radical cystectomy tumor stages with any node-positive (N1, N2, N3) or metastases-positive (M1) status. In addition, patients with N0 and M0 status with the following T-stages are also classified as pathologic non-responders: T2, T2a, T2b, T3, T3a, T3b, T4, T4a, T4b.

### **7.7.4. RFS survival analysis in each cohort**

Recurrence-free survival (defined as patients who are alive and without evidence of disease recurrence) from start of treatment to first documented recurrence will be estimated using Kaplan-Meier method for each treatment cohort and compared between the two cohorts using a log-rank test. The two-year recurrence-free survival estimates and confidence intervals will be provided for each cohort. If patients do not have recurrence tumor or death event then they are censored at the last RECIST assessment date.

The proportion of patients with recurrence-free survival at the two-year time point from registration will be displayed for each cohort.

### **7.7.5. Overall Survival (OS)**

OS is defined as the duration of time from start of treatment to time of death. Patients will be censored at the last date known alive. The Kaplan-Meier method for each treatment cohort and compared between the two cohorts using a log-rank test. The two-year OS estimates and confidence intervals will be provided for each cohort.

#### **7.7.6. IHC markers in relationship with tumor response in each cohort**

The marker levels in responders vs. non-responders will be compared by a t-test or Wilcoxon rank sum test as appropriate. In addition to evaluating expression on a continuous scale we will explore quantile values for each marker as potential thresholds to discretize the marker levels. The two-year RFS will then be compared between marker groups with a Fisher's exact test as well as via time-to-event analyses using standard methods for survival analysis. Changes in biomarker levels will be computed and compared between groups using a Wilcoxon rank sum test.

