**7.4.2.5. Proportion of patients who are alive and free of disease in each cohort at 2 years from registration.**

Analytic Plan for this secondary endpoint: Recurrence-free survival (defined as patients who are alive and without evidence of disease recurrence) from the time of registration will be estimated using Kaplan-Meier method for each treatment cohort and compared between the two cohorts using a log-rank test. The two-year disease-free survival estimates and confidence intervals will be provided for each cohort.

**7.4.2.6. The relationship between the expression of baseline IHC markers of interest (e.g. PD-1, PD-L1, PD-L2, NKG2D, KIR2DL1/2/3), and change in expression, for pathologic partial and complete tumor response (defined by cystectomy pathologic staging <pT2N0 and pT0N0, respectively), in patients treated with nivolumab and combination of nivolumab/lirilumab. To also compare the association of study cohort and pathologic response stratified by levels of expression of these biomarkers of interest.**

Analytic Plan for this secondary endpoint: As a general strategy, IHC marker levels in responders vs. non-responders will be compared by a t-test or Wilcoxon rank sum test as appropriate. In addition to evaluating expression on a continuous scale we will explore quantile values for each marker as potential thresholds to discretize the marker levels. The two-year RFS will then be compared between marker groups with a Fisher's exact test as well as via time-to-event analyses using standard methods for survival analysis. Changes in biomarker levels will be computed and compared between groups using a Wilcoxon rank sum test.

**7.4.2.7. The relationship between peripheral blood mononuclear cell (PBMC) T-cell subset status (%CD4+ T-cells, %CD8+ T-cells, %Treg T-cells, %Myeloid Derived Suppressor Cells, %Natural Killer cells, etc.) and change in status, as assessed by flow cytometry analysis, for pathologic partial and complete tumor response (defined by cystectomy pathologic staging < pT2N0 and pT0N0, respectively), in patients treated with nivolumab and combination of nivolumab/lirilumab.**

Analytic Plan for this secondary endpoint: The PBMC T-cell subset status in responders vs. non-responders will be compared by a t-test or Wilcoxon rank sum test as appropriate.

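### Two-year RFS is compared between marker groups by Fisher's exact test although RFS is censored; dropping patients censored before 24 months biases the two-year rate downward

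*SAP*

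**What the plan says.** **Marker groups.** SAP 7.7.6 states: "The two-year RFS will then be compared between marker groups with a" Fisher's exact test, and it adds time-to-event analyses beside that test. The IHC plan in SAP 7.4.2.6 and the exploratory plan in protocol 13.2.4.1 say the same. The marker groups come from exploring quantile cut-points. SAP 7.7.7 carries the strategy over to the PBMC analysis, but through a reference to a section 8.7.5 that the SAP does not contain.

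**The endpoint.** SAP 7.7.4 treats RFS as time-to-event. It "will be estimated using Kaplan-Meier method for each treatment cohort and compared between the two cohorts using a log-rank test". The censoring rule is: "If patients do not have recurrence tumor or death event then they are censored at the last RECIST assessment date". The section then adds: "The proportion of patients with recurrence-free survival at the two-year time point from registration will be displayed for each cohort".

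**Follow-up.** Patients are followed "for at least 2 years post-cystectomy or when study-wide follow-up ends per standard of care" (SAP 4.1). In protocol Section 11 the follow-up scans are at 3- to 6-month intervals at the physician's discretion, study imaging is no longer required once a new therapy starts, and contact may be by phone.

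**Missing data.** SAP 7.3 leaves missing data missing, without imputation. No section defines two-year RFS status for a patient censored before 24 months.

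**The concern.** Fisher's test needs every patient in the table to be classed as recurrence-free or not at 24 months. For a patient whose RFS time is censored at, say, month 18, that status is not observed. The patient must be dropped, counted as a failure or counted as event-free.

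The SAP's missing-data rule points to dropping. That is not neutral: a patient who recurs at month 10 is always kept, while one who was event-free when last scanned at month 18 is removed. Event-free patients are lost selectively, so the two-year rate falls below the true rate. If the marker groups differ in early censoring, the comparison shifts as well.

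At stake is the reading of the marker results on RFS, which could show a two-year difference, or hide one, because of the handling of a few patients.

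**Working it through.** The documents state no two-year RFS rate, censoring rate, power or alpha for this comparison, so there is no plan figure to reproduce. All event and censoring counts below are assumptions. From the documents come the group sizes (12 and 24, total 36), the censoring rule and the timings.

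**1. Can censoring fall before 24 months?** Treatment should start within 10 working days of registration (2 weeks), the second dose is at week 4, and surgery follows within 6 weeks. On schedule, cystectomy is at most 2 + 4 + 6 = 12 weeks after registration, or 84/30.4 = 2.8 months. Two years after cystectomy is therefore at most about 26.8 months after registration. The 2.8-month margin is shorter than a scan interval of 3 to 6 months, so a fully followed patient can have a last scan before month 24. An earlier end of study-wide follow-up, or the end of imaging at new therapy, adds further routes.

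**2. One group of 24.** Assume events at months 4, 7, 9, 12, 15 and 20, and censoring at months 10, 14, 18, 21 and 23. That leaves 24 − 6 − 5 = 13 patients event-free and observed at month 24.

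- Kaplan-Meier: (23/24)(22/23)(21/22)(19/20)(17/18)(15/16) = 0.736
- Censored patients excluded: 13/19 = 0.684
- Counted as failures: 13/24 = 0.542
- Counted as event-free: 18/24 = 0.750

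Exclusion is about 5 points below Kaplan-Meier. The full spread, 0.750 − 0.542 = 0.208, is just the assumed 5/24.

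**3. Expected bias over a range of censoring.** Assume exponential RFS with true two-year rate S = 0.60 and independent exponential censoring, with probability c of a censoring time before 24 months. Write a = −ln(0.60) and b = −ln(1 − c).

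- Observed event-free at 24 months: P = 0.60(1 − c)
- Observed censored early: K = [b/(a + b)](1 − P)
- Exclusion estimates P/(1 − K), failure P, and event-free P + K

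| c | K | Excluded | Failures | Event-free |
|---|---|---|---|---|
| 5% | 0.039 | 0.593 | 0.570 | 0.609 |
| 20% | 0.158 | 0.570 | 0.480 | 0.638 |
| 30% | 0.238 | 0.552 | 0.420 | 0.658 |

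Kaplan-Meier targets 0.60 in every row. Exclusion is biased downward by about 1 to 5 points.

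**4. Effect on Fisher's test.** Assume a median split of all 36 patients, 18 v 18, with two-sided p-values.

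| Events/censored early, by group | Excluded | Failures | Event-free |
|---|---|---|---|
| 4/2 v 10/4 | 0.026 | 0.018 | 0.086 |
| 4/4 v 11/1 | 0.073 | 0.315 | 0.041 |

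In the first row the tables are 4 and 12 v 10 and 4 under exclusion, 6 and 12 v 14 and 4 with censored patients as failures, and 4 and 14 v 10 and 8 with them as event-free. The rule moves p across 0.05, upward in one case and downward in the other. These counts carry no event times, so they show only the sensitivity to the rule, not what a log-rank test would give.

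**The case against.** **Early censoring may be rare.** Planned follow-up is at least two years after cystectomy, which falls later than two years from registration. With complete follow-up and timely scans, every status is known and the table agrees with Kaplan-Meier. This stands as a limit on the size. It does not remove the problem, because the scan schedule and stopping provisions allow early censoring and the plan has no rule for it.

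**A last scan is not the last information.** Follow-up is also clinical, phone contact is allowed, and dates of progression and survival are reported. A patient last scanned at month 22 may have a documented two-year status. This is fair and would reduce the number without a status. But the SAP does not say that such contacts define status, and using them only for the table would put Fisher and Kaplan-Meier on different data.

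**A valid analysis is already there.** Time-to-event methods stand beside Fisher in all three places, and protocol 13.2.4.1 says that the study is not powered for these analyses. The SAP does list the IHC analysis as secondary, but that endpoint concerns pathologic response and RFS is an addition to it. This stands and keeps the point minor.

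**Fisher is not redundant.** A log-rank test compares whole curves and Fisher a single time point. This stands, so the replacement should keep a two-year contrast for those who want one.

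**A stronger reading of SAP 7.7.4.** A reader might infer that the two-year proportion displayed by cohort is a raw count that must contradict the Kaplan-Meier estimate in the same section. The documents do not support that. SAP 7.4.2.5 and protocol 13.2.3.1 define the same endpoint, two years from registration, and give Kaplan-Meier from registration as its analysis. The sentence can be read as that estimate. What remains is unclear wording and a mixed time origin, since the rest of SAP 7.7.4 counts from start of treatment.

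**Conclusion.** The point holds and is minor. A Fisher comparison of two-year RFS does not suit an endpoint censored at the last RECIST assessment. Applied with the SAP's no-imputation rule it biases the two-year rate downward: by about 1 to 5 points for a true rate of 60% and a 5% to 30% chance of a censoring time before 24 months, and by about 5 points in the 24-patient example (68% v 74%). The p-value can cross 0.05 in either direction in groups of 18. These sizes rest on assumed counts, and on independent censoring for the expected bias. If nobody is censored before 24 months, the effect is nil.

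It would go too far to say that patients will certainly be censored early, or that the handling is wholly unstated, since SAP 7.3 implies exclusion. Nor does the point reach the comparison of the cohorts, which uses Kaplan-Meier and log-rank. The primary safety endpoint and the key secondary endpoint are untouched.

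**What to change.** 1. In SAP 7.4.2.6 and 7.7.6, replace the Fisher comparison with 24-month Kaplan-Meier estimates and confidence intervals by marker group, alongside the planned time-to-event analysis. If a two-year contrast is wanted, use the difference between the Kaplan-Meier estimates at 24 months. Align protocol 13.2.4.1 if it is next amended.
2. In SAP 7.7.4, state that the two-year proportion from registration is the Kaplan-Meier estimate, as SAP 7.4.2.5 and protocol 13.2.3.1 already specify, and use one time origin throughout.
3. In SAP 7.7.7, correct the cross-reference so that it is clear whether the change also covers PBMC.
4. If Fisher is kept, define two-year status, including whether clinical or phone contact after the last scan counts. Report the number without a status in each group, and give both extreme allocations as sensitivity analyses.

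The cost is a small SAP edit, logged in SAP Section 8, which now records no changes from the protocol, and the loss of a simple two-by-two table. In groups this small the confidence interval for a fixed-time difference is approximate and should be read that way. No new data are needed.
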